**Stopping Criteria for Dose Escalation:**

Dosing will be stopped if 1 (or more) of the following apply. Depending on the nature of the adverse events (AE)s, it could be decided to investigate a lower dose level (intermediate between the current and the prior one) in the next group.

1. If 1 or more subjects experiences a study drug-related serious adverse event (SAE), unblinding of the subject(s) will be done. If the subject(s) was (were) on active treatment, dosing will be stopped.
2. If 2 subjects in 1 dose group show the following findings in 2 consecutive postdose measurements within 24 hours and if unblinding reveals that both subjects received active treatment, dosing will be stopped:
  - a. ALT or AST  $\geq$  3 x ULN or,
  - b. ALT or AST  $\geq$  2 x ULN and ALT or AST  $\geq$  5 x baseline value or,
  - c. TBIL  $\geq$  2 x ULN
3. If 2 or more subjects in 1 cohort experience AEs of severe intensity or 4 or more subjects in 1 cohort experience AEs of moderate intensity, which are considered by the Principal Investigator (PI) and/or Sponsor to be possibly or probably related to the investigational product, and of clinical concern, and if unblinding reveals that these subjects received active treatment, dosing will be stopped.

stopped.

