### **3.3 Justification of the Study Design**

This is a study of safety, tolerability, PK, and PD of KM-819 administered orally to healthy adult and elderly subjects. A double-blind, placebo-controlled study is appropriate and standard for a SAD and MAD study. This design will minimize bias and provide reference data (i.e., data from placebo-treated subjects) which will aid in the interpretation of results.

Five SAD levels and four MAD levels are planned. The Principal Investigator (PI) and the Sponsor (both in a blinded state) will review available safety and PK data after each cohort to confirm whether it is safe to proceed with the next planned ascending dose, dose escalation should be stopped or the dose should be lowered or repeated in the subsequent cohort.

The safety assessments for the study are accepted measures for ensuring safety of patients during a clinical study. The times allowed for collection of PK/PD samples for KM-819 concentration are considered appropriate given the information available.

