### **3.5 Stopping Criteria for Dose Escalation**

Dosing will be stopped if 1 (or more) of the following apply. Depending on the nature of the AEs, it could be decided to investigate a lower dose level (intermediate between the current and the prior one) in the next group.

1. If 1 or more subjects experiences a study drug-related serious adverse event (SAE), unblinding of the subject(s) will be done. If the subject(s) was (were) on active treatment, dosing will be stopped.
2. If 2 subjects in 1 dose group show the following findings in 2 consecutive postdose measurements within 24 hours and if unblinding reveals that both subjects received active treatment, dosing will be stopped:
  - a. ALT or AST  $\geq 3 \times$  upper limit of normal (ULN) or,
  - b. ALT or AST  $\geq 2 \times$  ULN and ALT or AST  $\geq 5 \times$  baseline value or,
  - c. TBIL  $\geq 2 \times$  ULN
3. If 2 or more subjects in 1 cohort experience AEs of severe intensity or 4 or more subjects in 1 cohort experience AEs of moderate intensity, which are considered by the PI and/or Sponsor to be possibly or probably related to the investigational product, and of clinical concern, and if unblinding reveals that these subjects received active treatment, dosing will be stopped.

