##### *6.4.1.3.1 Seriousness*

A serious AE (SAE) is defined as any untoward medical occurrence that at any dose:

- Results in death;
- Is life-threatening;  
This means that the subject is at risk of death at the time of the event; it does not mean that the event hypothetically might have caused death if it were more severe;
- Requires inpatient hospitalization or prolongation of existing hospitalization;
- Results in persistent or significant disability or incapacity;
- Is a congenital anomaly or birth defect;
- Is an important medical event(s) that may not be immediately life-threatening or result in death or hospitalization but that may jeopardize the subject or require intervention to prevent one of the above outcomes. Examples of such events are intensive treatment in an emergency room or at home for allergic bronchospasm; blood dyscrasias or convulsions that do not result in hospitalization; or development of drug dependency or drug abuse.

Medical and scientific judgment should be exercised in deciding whether a case is serious and whether expedited reporting is appropriate.

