##### *6.4.1.3.2 Intensity*

The intensity of each AE must be assessed by the Investigator using one of the following categories, and recorded in the eCRF:

- Mild: The AE was transient and easily tolerated by the subject.
- Moderate: The AE caused discomfort and interferes with the subject's general condition.
- Severe: The AE caused considerable interference with the subject's general condition and may have been incapacitating.

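### Stopping criterion 3 counts moderate and severe AEs separately, so three moderate plus one severe does not stop dosing while four moderate does

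*Protocol*

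**What the plan says.** Protocol 3.5, No. 3 has two limbs joined by 'or': "2 or more subjects in 1 cohort experience AEs of severe intensity or 4 or more subjects in 1 cohort experience AEs of moderate intensity". The synopsis has the same second limb, "4 or more subjects in 1 cohort experience AEs of moderate intensity". Both limbs carry the same conditions. The principal investigator and/or sponsor must consider the events at least possibly related and of clinical concern, and the rule ends "and if unblinding reveals that these subjects received active treatment, dosing will be stopped".

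Protocol 6.4.1.3.2 defines mild, moderate and severe as separate grades, one per event: "The intensity of each AE must be assessed by the Investigator using one of the following categories". Neither document says that the moderate limb includes severe events, and the SAP adds no stopping rule.

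Two other criteria in Protocol 3.5 can stop dosing in the same cohort. No. 1 is the SAE rule: "If 1 or more subjects experiences a study drug-related serious adverse event (SAE), unblinding of the subject(s) will be done", with a stop if the subject was on active drug. No. 2 is the liver rule: "If 2 subjects in 1 dose group show the following findings in 2 consecutive postdose measurements within 24 hours". Protocol 3.3 also has the investigator and sponsor review blinded data after each cohort "to confirm whether it is safe to proceed with the next planned ascending dose".

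**The concern.** A stopping rule should be monotone: if a result triggers a stop, a worse result should trigger it too. Criterion 3 fails this in one place. Take four active subjects with qualifying moderate events; dosing stops. Now let one of the four have a severe event instead. The moderate count is 3, below 4, and the severe count is 1, below 2, so neither limb is met.

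The shared conditions do not explain the difference, because they apply equally to both limbs. What is lost is the automatic unblinding and stop in a first-in-human study of healthy volunteers. The decision then rests on discretion, in a case that is worse than one where the protocol leaves none.

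**Working it through.** The documents give no operating characteristics for this rule, so there is no figure of the plan's own to reproduce.

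**Inputs.** From Protocol 4.5.2: 6 active and 2 placebo subjects per cohort. From Protocol 3.5: thresholds of 2 severe and 4 moderate. Assumed, because the documents give none: per-subject probabilities pm and ps that the worst qualifying AE is moderate or severe.

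**Which outcomes are affected.** Let M and S be the numbers of active subjects whose worst qualifying AE is moderate or severe.
- As written: stop if S ≥ 2 or M ≥ 4.
- Pooled: stop if S ≥ 2 or M + S ≥ 4.

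Enumerating every split of 6 subjects, the two rules differ only at (M, S) = (3, 1). For comparison, (4, 0), (4, 1) and (2, 2) meet both.

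**Probability of that outcome.** The multinomial coefficient is 6!/(3!·1!·2!) = 60, so P = 60 · pm³ · ps · (1 − pm − ps)².
- (0.05, 0.01): 60 × 0.000125 × 0.01 × 0.8836 = 0.00007
- (0.15, 0.03): 60 × 0.003375 × 0.03 × 0.6724 = 0.0041
- (0.20, 0.05): 60 × 0.008 × 0.05 × 0.5625 = 0.0135
- (0.30, 0.10): 60 × 0.027 × 0.10 × 0.36 = 0.0583

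For the last three pairs, criterion 3 alone is met with probability 1.8% as written against 2.2% pooled, 5.0% against 6.3%, and 18.4% against 24.2%.

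**Discount for other routes to a stop.** At given rates these figures are upper bounds, because a (3, 1) cohort can still be stopped in three ways:
- The severe event is a drug-related SAE and criterion 1 applies. Protocol 6.4.1.3.1 counts as serious an event that "Requires inpatient hospitalization or prolongation of existing hospitalization", so overlap with severe events is likely.
- The liver rule is met. This route is not discounted below.
- The subject with the severe event also has a separate qualifying moderate event, which brings the moderate count to 4.

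Let s be the share of severe events that are drug-related SAEs, and q the share of the remaining severe-event subjects who also have a qualifying moderate event. Multiply P by (1 − s)(1 − q).

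| Assumed (pm, ps) | No discount | s = 0.5, q = 0 | s = q = 0.5 |
|---|---|---|---|
| (15%, 3%) | 0.4% | 0.2% | 0.1% |
| (20%, 5%) | 1.4% | 0.7% | 0.3% |
| (30%, 10%) | 5.8% | 2.9% | 1.5% |

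**Share of all stops.** At s = q = 0.5, the chance of a stop under criteria 1 and 3 together, as written against pooled, is 9.64% against 9.75%, 16.82% against 17.15%, and 36.72% against 38.18%. The difference is 1.0%, 2.0% and 3.8% of the pooled stops.

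**Extra unblinding under the pooled rule.** The count that triggers unblinding is taken over all 8 subjects. With assumed placebo rates of (5%, 1%), the only added trigger is again 3 moderate plus 1 severe, with probability 0.67%, 1.84% and 6.52%. The part in which all four are active is P × 0.94² = 0.36%, 1.19% and 5.15%. The remainder, 0.31%, 0.65% and 1.36%, includes a placebo subject, so unblinding would end without a stop. These figures carry no discount.

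**The case against.** The strongest reply is that the gap changes little in practice. Four points support it.
- Criterion 3 is not mechanical. In a (3, 1) cohort the investigator and sponsor have already judged four subjects' events related and of concern, and are unlikely to escalate because the count fell between two limbs.
- The review in Protocol 3.3 can stop, lower or repeat the dose. Protocol 3.4 holds each Part A escalation until data through Day 4 have been reviewed. Protocol 4.3, 5.5 and 9.10 allow individual discontinuation, discretionary unblinding and termination of the study.
- A stop under criterion 3 need not end escalation, since Protocol 3.5 allows an intermediate lower dose in the next group.
- In Part A only one active subject is in the sentinel pair, so at least three of the four come from the main group and most doses have been given by then. Ongoing dosing is at stake mainly in Part B.

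All of this stands, and it limits the consequence. It does not repair the rule. The same discretion exists for four moderate events, and there the protocol still made the stop mandatory. The reading that moderate is a floor is natural, but the text does not say it, and Protocol 9.8 requires the protocol to be followed exactly.

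A further objection is that the unblinding cost is undiscounted while the smallest benefit figures are discounted. On that mixed basis, futile unblinding (0.31%, 0.65%) exceeds the gain (0.10%, 0.34%) at the two lower rate pairs. Compared without discounts, the gain is 0.41%, 1.35% and 5.83% against 0.31%, 0.65% and 1.36%. Applying the same factor of 0.25 to both, as an approximation, gives 0.10%, 0.34% and 1.46% against 0.08%, 0.16% and 0.34%. The gain is larger at all three pairs.

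**Conclusion.** The concern holds, as a minor point. On the literal wording, criterion 3 is not monotone at exactly one outcome among 6 active subjects: three moderate and one severe. That conclusion follows from the text and needs no assumed rates.

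The size does depend on assumptions: the AE rates, independence between subjects, and the values of s and q, none of which has a source in the documents. Over the three rate pairs the gap affects at most 0.4% to 5.8% of cohorts, and 0.1% to 1.5% with both discounts. It would be larger at higher AE rates. No endpoint, estimate or sample size is affected.

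**What to change.** In Protocol 3.5, No. 3, and in the synopsis, add two words to the second limb so that it counts subjects with AEs of *at least moderate* intensity. Leave the thresholds of 2 and 4, the relatedness and clinical-concern conditions, and the closing clause on unblinding and active treatment as they are.

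This needs a protocol amendment but no new data or analysis. The chance of a stop rises only in the (3, 1) outcome, by 0.007% per cohort at low rates of (5%, 1%). The extra unblinding is the amount shown in the check above.

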### ***3.5.1 PK stopping criteria***

Due to the liver damage (higher ALT, ALP, GGT, and enlargement in common bile duct in liver) reported in one male dog following multiple dosing at 2000 mg/kg for 7 days, and NOAEL in male and female beagle dog at 1000 mg/kg/day for 14 days, the decision to escalate to the next planned dose will be based on review of PK exposure data from previous dose cohort(s). This will involve use of best available modeling practices of the observed AUC (i.e.,  $AUC_{\text{tau}}$  or  $AUC_{0-\infty}$ ) and  $C_{\text{max}}$  from each dose, resulting in a predictive distribution of AUC and  $C_{\text{max}}$  at higher dose levels. If predicted mean AUC and  $C_{\text{max}}$  for the next dose level is higher than 41.3 ug.h/mL and 9.3 ug/mL, respectively, then the dose escalation will stop and the Sponsor and PI will need to review the totality of data, including safety and PK before make any dose escalation decision. This PK stopping criteria are based on dog 2-Week study NOAEL exposure at 1000 mg/kg/day (the most conservative species and gender).

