#### **PK stopping criteria**

The decision to escalate to the next planned dose will also be based on review of PK exposure data from previous dose cohort(s). All available PK data will be used to estimate the expected exposures (AUC and  $C_{max}$ ) of the next dose level using modeling. If predicted mean AUC and  $C_{max}$  for the next dose level is higher than 41.3 ug.h/mL and 9.3 ug/mL, respectively, then the dose escalation will stop and the Sponsor and PI will need to review the totality of data, including safety and PK before make any dose escalation decision.

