**Table 3-1: Dose Groups for Part A**

KM-819 Dose (mg)	Subjects on KM-819 (n)	Subjects on Placebo (n)	Total Subjects in Group (n)	Age Group
10†	6	2	8	Young adult male subjects
30†	6	2	8	
100†	6	2	8	
200†	6	2	8	
400†	6	2	8	
200	6	2	8	Elderly male or post-menopausal female subjects

† Doses between the current planned range may be assigned or a dose may be repeated depending on safety, tolerability, and pharmacokinetic data from previous subjects and cohorts.

All subjects will undergo a Screening period of up to 28 days and a 3-day Confinement period when they are hospitalized for study activities (Day -1 to Day 3). Subjects are required to return for outpatient visits on Day 4, Day 7, and for Follow-up Visit on Day 14. See Figure 3-1 for Part A SAD study design.

\*: Baseline

\*\*: Randomization and study drug administration

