**Table 3-2: Dose Groups for Part B**

KM-819 Dose (mg)	Subjects on KM-819 (n)	Subjects on placebo (n)	Total Subjects in Group (n)	Age Group
30†	6	2	8	Young adult male subjects
100†	6	2	8	
200†	6	2	8	
400†	6	2	8	
200	6	2	8	Elderly male or post-menopausal female subjects

† Doses between the current planned range may be assigned depending on safety, tolerability, and pharmacokinetic data from previous subjects and cohorts.

All subjects will undergo a Screening period of up to 28 days and an 8-day Confinement period when they are hospitalized for study activities (Day -1 to Day 8). Subjects are required to return for a Follow-up Visit on Day 14. See Figure 3-2 for Part B MAD study design.

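### The PK stopping rule as worded needs AUC and Cmax both over their limits; under the protocol's own predicted PK it never triggers in 10–400 mg, although predicted AUC at 400 mg is 1.16 times its limit

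*Protocol*

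**What the plan says.** Protocol Section 3.5.1 has AUC and Cmax from completed cohorts modelled to predict exposure at the next dose. It then sets a rule on the predicted means: if AUC and Cmax "for the next dose level is higher than 41.3 ug.h/mL and 9.3 ug/mL, respectively, then the dose escalation will stop". The PK stopping criteria in the synopsis are built the same way: "for the next dose level is higher than 41.3 ug.h/mL and 9.3 ug/mL, respectively".

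Section 3.5.1 gives the source of the limits: "This PK stopping criteria are based on dog 2-Week study NOAEL exposure at 1000 mg/kg/day". It motivates them by liver damage in one male dog dosed at 2000 mg/kg for 7 days. The consequence of a breach is a stop, after which "the Sponsor and PI will need to review the totality of data, including safety and PK before make any dose escalation decision".

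The parent Section 3.5 opens with "Dosing will be stopped if 1 (or more) of the following apply" and then lists three numbered safety rules.

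Planned doses run from 10 to 400 mg (Part A, single dose) and from 30 to 400 mg once daily for 7 days (Part B). Other doses must lie inside those ranges. The footnote to Table 3-1 reads "Doses between the current planned range may be assigned or a dose may be repeated", and the footnote to Table 3-2 reads "Doses between the current planned range may be assigned depending on safety, tolerability, and pharmacokinetic data".

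The SAP does not restate the exposure limits.

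**The concern.** *Respectively* pairs each parameter with its own limit. It does not turn *and* into *or*, and no other text says that one breach is enough. Section 3.5 itself separates the two words: liver rule 2 joins its alternatives a, b and c with *or*, and uses *and* inside 2b for a joint condition. A reader who carries that usage into 3.5.1 will treat the PK rule as joint.

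A joint rule does not fit its purpose. If the limits mark the exposure tolerated by the dog, exposure is above that level once either measure exceeds its limit.

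This is the only numeric exposure limit in a first-in-human trial. If one of the two measures is far from its limit throughout the dose range, the joint rule cannot act on the other.

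**Working it through.** **Inputs.** From Section 5.3: CL = 2.93 L/h, V = 39.2 L, F = 0.35, one compartment, first-order absorption and elimination. From Section 3.5.1: limits of 41.3 ug.h/mL and 9.3 ug/mL. The protocol gives no absorption rate constant, so instant absorption is used as an upper bound on Cmax.

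**Reproducing the protocol's figure.** k = 2.93/39.2 = 0.0747 /h, and half-life = ln 2/k = 9.27 h, as Section 5.3 states.

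**Formulas.**
- AUC (0–∞ after one dose, or over a dosing interval at steady state) = F × dose/CL.
- Single-dose Cmax ≤ F × dose/V.
- Once-daily Cmax ≤ that value × 1/(1 − exp(−24k)) = that value × 1.199.

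| Dose (mg) | AUC (ug.h/mL) | AUC / 41.3 | Cmax bound, single (ug/mL) | Cmax bound, once daily (ug/mL) |
|---|---|---|---|---|
| 10 | 1.19 | 0.03 | 0.09 | not planned |
| 30 | 3.58 | 0.09 | 0.27 | 0.32 |
| 100 | 11.95 | 0.29 | 0.89 | 1.07 |
| 200 | 23.89 | 0.58 | 1.79 | 2.14 |
| 400 | 47.78 | 1.16 | 3.57 | 4.28 |

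At 400 mg the Cmax bounds are 3.57/9.3 = 38% and 4.28/9.3 = 46% of the limit. Slower absorption only lowers Cmax: with an assumed rate constant of 0.3 to 5 /h it is 2.25–3.35 (single) or 2.87–4.03 ug/mL (once daily).

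**Doses at which the limits are reached.**
- AUC: 41.3 × 2.93/0.35 = 346 mg.
- Cmax: 9.3 × 39.2/0.35 = 1042 mg single dose, or 1042/1.199, about 868 mg, once daily.

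The joint rule therefore needs more than about 868 mg once daily or 1042 mg single dose, both outside the plan. An either-limit rule triggers before 400 mg and not at 200 mg.

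**Sensitivity at 400 mg.**
- *Bioavailability.* AUC exceeds its limit if F is above 41.3 × 2.93/400 = 0.303. With the animal values in Section 1.2.1.3 (28.9%, 32.3%, 35.97%), AUC is 39.5, 44.1 and 49.1 ug.h/mL, or 0.96, 1.07 and 1.19 times the limit. At 28.9% the two readings agree.
- *Half-life at the animal oral values (4.96–6.06 h), smaller V with CL kept.* V is 21.0–25.6 L and AUC stays at 47.8. Cmax is at most 5.5–6.7 (single) or 5.8–6.9 ug/mL (once daily). The joint rule still does not fire; it would need a half-life below about 3.6 h.
- *The same half-lives, higher CL with V kept.* CL is 4.48–5.48 L/h and AUC is 25.6–31.2. Neither reading triggers.
- *Peak shape (assumption: 70 kg, animal oral peak per absorbed mg/kg carried over).* F × dose/Cmax is 0.269 and 0.305 L/kg in dogs and 0.462 L/kg in rats. Absorbed dose is 0.35 × 400/70 = 2.0 mg/kg. Cmax is then 4.3–7.4 (single) or 5.2–8.9 ug/mL (once daily, × 1.199): under 9.3, but close at the top end.
- *AUC definition.* If the first-dose AUC over 24 h were used instead, it would be at most 47.78 × (1 − exp(−24k)) = 39.8, just under the limit. Section 3.5.1 names the dosing-interval AUC or AUC to infinity; the calculation takes the former at steady state.

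**The case against.** **The text is ambiguous rather than wrong.** The singular verb and *respectively* could suggest that each parameter is judged separately, and 3.5.1 sits under a lead-in that requires only one criterion. The sponsor may well have meant either limit. But the lead-in most naturally covers rules 1–3. Even if it reached 3.5.1, it would make the PK rule one item in the list without saying how the two limits combine inside that item. If either limit was intended, the text should say so.

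**Little is lost in practice.** A breach does not bar 400 mg; it forces a review. Section 3.3 already has the Principal Investigator and the sponsor review safety and PK after each cohort, Section 3.4 requires review before escalation in Part A, and liver enzymes have their own rule. This stands, and it limits the consequence to the loss of a binding trigger at one dose step.

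**The rule will run on observed human data.** This also stands. Lower bioavailability or higher clearance removes the difference. So would less-than-proportional exposure: dog Cmax rose only from 6.01 to 9.48 ug/mL when the dose doubled from 5 to 10 mg/kg. A shortfall of 1 − 41.3/47.78, about 14%, from proportionality would bring AUC at 400 mg down to the limit.

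**The peak-shape check depends on 70 kg.** It does. With the highest dog peak and the 1.199 factor, once-daily Cmax passes 9.3 below about 67 kg (140/0.2687/67 × 1.199 = 9.3), and the joint rule would then fire. This weakens that side check only. The result under the Section 5.3 model uses no body weight.

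**Conclusion.** The concern holds. As written, the decision rule requires both limits to be exceeded. Under the protocol's own prediction it cannot trigger at any planned dose, while an either-limit rule stops for review before 400 mg. At 200 mg and below the two readings agree.

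The size of the AUC excess, 1.16 times the limit, rests on F = 35%, CL = 2.93 L/h and dose-proportional exposure, and it is not large. The wording defect does not depend on those values; only its effect in this trial does. It should be fixed, because following the text literally could pass over a predicted AUC above the dog NOAEL at the highest dose step.

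**What to change.** In Section 3.5.1 and in the synopsis, restate the rule along these lines:

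> Escalation stops if the predicted mean AUC at the next dose is above 41.3 ug.h/mL, or if the predicted mean Cmax is above 9.3 ug/mL. Either breach alone is sufficient. The Sponsor and PI then review all safety and PK data before deciding whether to escalate.

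This changes one sentence in two places and needs no extra data. The cost is that a review pause before 400 mg becomes more likely.
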